Chills	Symptoms causing no or minimal interference with usual social & functional activities	Symptoms causing greater than minimal interference with usual social & functional activities	Symptoms causing inability to perform usual social & functional activities	NA
Fatigue Malaise	Symptoms causing no or minimal interference with usual social & functional activities	Symptoms causing greater than minimal interference with usual social & functional activities	Symptoms causing inability to perform usual social & functional activities	Incapacitating fatigue/malaise symptoms causing inability to perform basic self-care functions
Fever (nonaxillary)	37.7°C to 38.6°C 99.8°F to 101.5°F	38.7°C to 39.3°C 101.6°F to 102.8°F	39.4°C to 40.5°C 102.9°F to 104.9°F	> 40.5°C > 104.9°F
Pain- Indicate Body Site See also Injection Site Pain, Headache, Arthralgia, and Myalgia	Pain causing no or minimal interference with usual social & functional activities	Pain causing greater than minimal interference with usual social & functional activities	Pain causing inability to perform usual social & functional activities	Disabling pain causing inability to perform basic self-care functions OR Hospitalization (other than ER visit) indicated
Unintentional Weight Loss	NA	5% to 9% loss in body weight from baseline	10% to 19% loss in body weight from baseline	≥ 20% loss in body weight from baseline OR Aggressive intervention indicated [eg, tube feeding or total parenteral nutrition]

INJECTION SITE REACTION				
	Grade 1	Grade 2	Grade 3	Grade 4
Injection Site Pain (pain without touching) Or Tenderness (pain when area is touched)	Pain/tenderness causing no or minimal limitation of use of limb	Pain/tenderness limiting use of limb OR Pain/tenderness causing greater than minimal interference with usual social & functional activities	Pain/tenderness causing inability to perform usual social & functional activities	Pain/tenderness causing inability to perform basic self-care function OR Hospitalization (other than ER visit) indicated for management of pain/tenderness
Injection Site Reaction (Localized), > 15 Years  Pediatric ≤ 15 Years	Erythema OR Induration of 5 × 5 cm to 9 × 9 cm (or 25–81 × cm  )  Erythema OR Induration OR Edema present but ≤ 2.5 cm diameter	Erythema OR Induration OR Edema > 9 cm any diameter (or > 81 cm  )  Erythema OR Induration OR Edema > 2.5 cm diameter but < 50% surface area of the extremity segment (eg, upper arm/thigh)	Ulceration OR Secondary infection OR Phlebitis OR Sterile abscess OR Drainage  Erythema OR Induration OR Edema involving ≥ 50% surface area of the extremity segment (eg, upper arm/thigh) OR Ulceration OR Secondary infection OR Phlebitis OR Sterile abscess OR Drainage	Necrosis (involving dermis and deeper tissue)  Necrosis (involving dermis and deeper tissue)
Pruritis Associated with Injection See also Skin: Pruritis (itching—no skin lesions)	Itching localized to injection site AND Relieved spontaneously or with < 48 h treatment	Itching beyond the injection site but not generalized OR Itching localized to injection site requiring ≥ 48 h treatment	Generalized itching causing inability to perform usual social & functional activities	NA

ENDOCRINE/METABOLIC				
	Grade 1	Grade 2	Grade 3	Grade 4
Lipodystrophy (eg, back of neck, breasts, abdomen)	Detectable by study participant or caregiver (for young children and disabled adults)	Detectable on physical exam by health care provider	Disfiguring OR Obvious changes on casual visual inspection	NA
Diabetes Mellitus	NA	New onset without need to initiate medication OR Modification of current meds to regain glucose control	New onset with initiation of indicated med OR Diabetes uncontrolled despite treatment modification	Life-threatening consequences (eg, ketoacidosis, hyperosmolar non-ketotic coma)
Gynecomastia	Detectable by study participant or caregiver (for young children and disabled adults)	Detectable on physical exam by health care provider	Disfiguring OR Obvious on casual visual inspection	NA
Hyperthyroidism	Asymptomatic	Symptomatic causing greater than minimal interference with usual social & functional activities OR Thyroid suppression therapy indicated	Symptoms causing inability to perform usual social & functional activities OR Uncontrolled despite treatment modification	Life-threatening consequences (eg, thyroid storm)
Hypothyroidism	Asymptomatic	Symptomatic causing greater than minimal interference with usual social & functional activities OR Thyroid replacement therapy indicated	Symptoms causing inability to perform usual social & functional activities OR Uncontrolled despite treatment modification	Life-threatening consequences (eg, myxedema coma)
Lipoatrophy (eg, fat loss from the face, extremities, buttocks)	Detectable by study participant or caregiver (for young children and disabled adults)	Detectable on physical exam by health care provider	Disfiguring OR Obvious on casual visual inspection	NA

GENITOURINARY				
	Grade 1	Grade 2	Grade 3	Grade 4
Intermenstrual Bleeding (IMB)	Spotting observed by participant OR Minimal blood observed during clinical or colposcopic exam	Intermenstrual bleeding not greater in duration or amount than usual menstrual cycle	Intermenstrual bleeding greater in duration or amount than usual menstrual cycle	Hemorrhage with life-threatening hypotension OR Operative intervention indicated
Urinary Tract obstruction (eg, stone)	NA	Signs or symptoms of urinary tract obstruction without hydronephrosis or renal dysfunction	Signs or symptoms of urinary tract obstruction with hydronephrosis or renal dysfunction	Obstruction causing life-threatening consequences

INFECTION				
	Grade 1	Grade 2	Grade 3	Grade 4
Infection (any other than HIV infection)	Localized, no systemic antiꞑbial treatment indicated AND Symptoms causing no or minimal interference with usual social & functional activities	Systemic antiꞑbial treatment indicated OR Symptoms causing greater than minimal interference with usual social & functional activities	Systemic antiꞑbial treatment indicated AND Symptoms causing inability to perform usual social & functional activities OR Operative intervention (other than simple incision and drainage) indicated	Life-threatening consequences (eg, septic shock)

**Basic Self-care Functions:** Activities such as bathing, dressing, toileting, transfer/movement, continence, and feeding.

**Usual Social & Functional Activities:** Adaptive tasks and desirable activities, such as going to work, shopping, cooking, use of transportation, pursuing a hobby, etc.

## **Appendix 5. Pregnancy Precautions, Definition for Female of Childbearing Potential, Definition of Male Fertility and Contraceptive Requirements**

### **1) Definitions**

#### **a. Definition of Childbearing Potential**

For the purposes of this study, a female born subject is considered of childbearing potential following the initiation of puberty (Tanner stage 2) until becoming post-menopausal, unless permanently sterile or with medically documented ovarian failure.

Women are considered to be in a postmenopausal state when they are  $\geq 54$  years of age with cessation of previously occurring menses for  $\geq 12$  months without an alternative cause.

Permanent sterilization includes hysterectomy, bilateral oophorectomy, or bilateral salpingectomy in a female subject of any age.

#### **b. Definition of Male Fertility**

For the purposes of this study, a male born subject is considered to be fertile after the initiation of puberty unless permanently sterile by bilateral orchidectomy or medical documentation.

### **2) Contraception Requirements for Male Subjects**

During the study, male subjects with female partners of childbearing potential should use condoms when engaging in intercourse of reproductive potential.

Male subjects must agree to refrain from sperm donation from first study drug dose until after the end of relevant systemic exposure.

### **3) Unacceptable Birth Control Methods**

Birth control methods that are unacceptable include periodic abstinence (e.g., calendar, ovulation, symptothermal, post-ovulation methods), withdrawal (coitus interruptus), spermicides only, and lactational amenorrhea method (LAM). Female condom and male condom should not be used together.

**Appendix 6. Definitions of Stage 3 Opportunistic Illnesses in HIV  
(CDC Guidelines)**

1. Candidiasis of bronchi, trachea, or lungs
2. Candidiasis of esophagus
3. Cervical cancer, invasive
4. Coccidioidomycosis, disseminated or extrapulmonary
5. Cryptococcosis, extrapulmonary
6. Cryptosporidiosis, chronic intestinal (> 1 month duration)
7. Cytomegalovirus disease (other than liver, spleen or nodes)
8. Cytomegalovirus retinitis (with loss of vision)
9. Encephalopathy, HIV-related
10. Herpes simplex: chronic ulcer(s) (> 1 month duration); or bronchitis, pneumonitis or esophagitis
11. Histoplasmosis, disseminated or extrapulmonary
12. Isosporiasis, chronic intestinal (> 1 month duration)
13. Kaposi's sarcoma
14. Lymphoma, Burkitt's (or equivalent term)
15. Lymphoma, immunoblastic (or equivalent term)
16. Lymphoma, primary, of brain
17. *Mycobacterium avium* complex or *Myobacterium kansasii*, disseminated or extrapulmonary
18. *Mycobacterium tuberculosis*, of any site, pulmonary, disseminated or extrapulmonary
19. *Mycobacterium*, other species or unidentified species, disseminated or extrapulmonary
20. Pneumocystis jirovecii (previously known as "*Pneumocystis carinii*") pneumonia
21. Pneumonia, recurrent
22. Progressive multifocal leukoencephalopathy

23. *Salmonella* septicemia, recurrent

24. Toxoplasmosis of brain

25. Wasting syndrome attributed to HIV infection

CDC Stage-3-Defining Opportunistic Illnesses in HIV Infection - 2014 {[Selik 2014](#)}

CSR	clinical study report
DOB	date of birth
E/C/F/TAF	elvitegravir /cobicistat emtricitabine/ tenofovir alafenamide; Genvoya; GEN
ECG	electrocardiogram
eCRF	electronic case report form
eGFR	estimated glomerular filtration rate
eGFR _{CKD-EPI, cysC}	estimated glomerular filtration rate using CKD-EPI (cystatin C) formula
eGFR(CG)	estimated glomerular filtration rate using Cockcroft-Gault formula
EQ-5D	EuroQol 5D patient questionnaire
FACIT-F	functional assessment of chronic illness therapy - fatigue
FAS	full analysis set
FDA	Food and Drug Administration
FDC	fixed dose combination
FTC/TDF	single-tablet regimen of emtricitabine 200 mg/ tenofovir disoproxil fumarate 300 mg
FTC	Emtricitabine; F
GFR	glomerular filtration rate
Gilead	Gilead Sciences, Inc.
HCV	hepatitis C virus
HDL	high density lipoprotein
HIV-1	human immunodeficiency virus (Type 1)
HIVTSQc	HIV treatment satisfaction change
HIVTSQs	HIV treatment satisfaction status
HLGT	high level group term
HLT	high level term
INR	international normalized ratio
LDL	low density lipoprotein
LLT	lowest level term

MedDRA	Medical Dictionary for Regulatory Activities
NLP	natural language processing
PK	pharmacokinetic
PT	preferred term
PT	prothrombin time
PVE	pharmacovigilance and epidemiology
Q	quartile
Q1	first quartile
Q3	third quartile
RBP	retinol binding protein
RNA	ribonucleic acid
SAE	serious adverse events
SAP	statistical analysis plan
SD	standard deviation
SE	standard error
SF-36	Short Form 36 Health Survey
SOC	system organ class
TAF	tenofovir alafenamide
TDF	tenofovir disoproxil fumarate
TEAE	treatment-emergent AE
TFL	tables, figures, and listings
ULN	upper limit of normal
UP	urine protein
UPCR	urine protein to urine creatinine ratio
VAS	visual analog scale
WHO	World Health Organization

1. INTRODUCTION

This statistical analysis plan (SAP) describes the statistical analysis methods and data presentations to be used in tables, figures, and listings (TFLs) of the final analysis for Study GS US-380-4449, which will be performed when all subjects have completed the study or prematurely discontinued from the study. The Week 24 analyses and the Week 48 analyses will not be repeated for this final analysis.

This SAP is based on the study protocol amendment 2 dated 18 December 2018 and the electronic case report form (eCRF). The SAP will be finalized before the data finalization for the final analysis. Any changes made after the finalization of the SAP will be documented in the clinical study report.

1.1. Study Objectives

The primary objective of this study is:

- To characterize the virologic efficacy of switching virologically suppressed subjects on an Elvitegravir/Cobicistat/Emtricitabine/Tenofovir Alafenamide (E/C/F/TAF) fixed dose combination (FDC) regimen or Tenofovir Disoproxil Fumarate (TDF)-containing regimen to bictegravir (BIC; B) /emtricitabine (FTC; F) /tenofovir alafenamide (B/F/TAF) FDC defined by HIV-1 RNA < 50 copies/mL at Week 24.

The secondary objectives of this study are:

- To characterize the safety and tolerability of switching to B/F/TAF FDC from an E/C/F/TAF FDC or TDF-containing regimen through Week 96.
- To characterize the virologic efficacy of switching to B/F/TAF FDC defined by HIV-1 RNA < 50 copies/mL at Week 48, Week 72 and Week 96.

1.2. Study Design

Design Configuration and Subject Population

GS-US-380-4449 is an open-label, multicenter, single arm study to evaluate switching from either E/C/F/TAF FDC or TDF and FTC-containing ‘backbone’ regimen plus a third agent to B/F/TAF FDC in virologically-suppressed (HIV-1 RNA < 50 copies/mL), HIV-1 infected subjects aged \geq 65 years.

Eligible subjects who complete GS-US-292-1826 through Week 48 and are at least 65 years old at the screening visit will be allowed to enter. Subjects not previously participating in GS-US-292-1826 will be able to enroll as long as they meet all eligibility criteria.

Treatment Groups

There is one treatment group: FDC of BIC 50 mg/FTC 200 mg/TAF 25 mg (B/F/TAF) administered orally, once daily, without regard to food (approximate n = 80).

Key Eligibility Criteria

Medically stable HIV-1 infected subjects who meet the following criteria:

- Age \geq 65 years
- Currently receiving an antiretroviral (ARV) regimen of E/C/F/TAF FDC (or FTC/TDF + 3rd agent if currently or previously participated in GS-US-292-1826) for \geq 3 months
- Documented plasma HIV-1 RNA levels $<$ 50 copies/mL during treatment with E/C/F/TAF (or FTC/TDF + 3rd agent if currently or previously participated in GS-US-292-1826) for the last 2 visits preceding the Screening Visit (or undetectable HIV-1 RNA level according to the local assay being used if the limit of detection is \geq 50 copies/mL)
- Adequate renal function, an estimated glomerular filtration rate (eGFR) \geq 30 mL/min according to the Cockcroft-Gault formula for creatinine clearance (eGFR_{CG})

Study Periods / Phases

Subjects will be treated for at least 96 weeks. CCI [REDACTED]

Subjects who complete the study through the Week 96 Visit and do not continue participation in the study will be required to return to the clinic 30 days after the Week 96 Visit for a 30 Day Follow-Up Visit.

Schedule of Assessments

After screening procedures, study visits will occur at Day 1, Weeks 4, 12, 24, 36, 48, 60, 72, 84 and 96.

Laboratory analyses (including chemistry, hematology, and urinalysis), HIV-1 RNA, CD4+ cell count, assessment of adverse events (AEs), and concomitant medications, and complete or symptom directed physical examinations will be performed at all study visits.

Blood and urine for selected evaluations of renal safety, inflammation, and platelet and coagulation function will be collected at Day 1, Weeks 4, 12, 24, 48, 60, 72, 84, and 96. A portion of the biomarker blood sample obtained at Day 1, Weeks 4, 12, 24, 48, 60, 72, 84, and 96 may be utilized to assess study drug pharmacokinetics (PK). This will be a random sample with the date and time of the subject's last medication dose recorded.

Site and/or Stratum Enrollment Limits

Approximately 30 study sites in Europe participated. Approximately 80 subjects who meet the eligibility criteria will be enrolled in the study.

Study Duration

The treatment duration specified in the protocol was 96 weeks CCI [REDACTED] However, all subjects will discontinue the study at Week 96; therefore treatment duration will be up to 96 weeks, followed by a 30 day follow-up.

1.3. Sample Size and Power

The sample size is based on feasibility of conducting a study with ≥ 65 year old subjects.

2. TYPE OF PLANNED ANALYSIS

2.1. Week 24 Analysis

The Week 24 analysis was conducted after all subjects either completed their Week 24 visit or prematurely discontinued from the study drug.

2.2. Week 48 Analysis

The Week 48 analysis was conducted after all subjects either completed their Week 48 visit or prematurely discontinued from the study drug.

2.3. Final Analysis

The final statistical analysis will be conducted after all subjects either complete the study or prematurely discontinue from the study.

This SAP describes the analysis plan for the final analysis.

3. GENERAL CONSIDERATIONS FOR DATA ANALYSES

Analysis results will be presented using descriptive statistics. For categorical variables, the number and percentage of subjects in each category will be presented; for continuous variables, the number of subjects (n), mean, standard deviation (SD) or standard error (SE), median, first quartile (Q1), third quartile (Q3), minimum, and maximum will be presented.

By-subject listings will be presented for all subjects in the All Enrolled analysis set unless otherwise specified, and sorted by subject ID number, visit date, and time (if applicable). Data collected on log forms, such as AEs, will be presented in chronological order within a subject.

In general, age (in years) on the date of the first dose of study drug will be used for analyses and presentation in listings. For enrolled but never dosed subjects, age calculated using the date of enrollment will be used. For screen failures, age calculated using the date of the informed consent was signed will be used. Because only birth year is collected on the eCRF, and because age was not collected at Day 1 for this study, “01 January” will be used for the unknown birth day and month for the purpose of age calculation.

3.1. Analysis Sets

Analysis sets define the subjects to be included in an analysis. Analysis sets and their definitions are provided in this section. Subjects included in each analysis set will be determined before data finalization. The analysis set will be included as a subtitle of each table, figure, and listing. A summary of the number and percentage of subjects in each analysis set will be provided.

3.1.1. All Enrolled Analysis Set

The **All Enrolled Analysis Set** will include all subjects who were enrolled into the study. This is the primary analysis set for by-subject listings unless otherwise specified.

3.1.2. Full Analysis Set

The **Full Analysis Set** includes all subjects who (1) were enrolled and received at least 1 dose of study drug, and (2) do not have major protocol violations. This is the primary analysis set for all efficacy analyses.

The major protocol violations include

- ARV regimen at study entry other than E/C/F/TAF FDC (or FTC/TDF + 3rd agent if currently or previously participated in GS-US-292-1826)
- ARV regimen at study entry for < 3 months

3.1.3. Safety Analysis Set

The **Safety Analysis Set** includes all subjects who were enrolled and received at least 1 dose of study drug. This is the primary analysis set for all safety analyses.

3.2. Subject Grouping

There is one subject group: B/F/TAF.

3.3. Strata and Covariates

There is no stratification for analysis.

3.4. Examination of Subject Subgroups

No subgroup analyses are planned.

3.5. Multiple Comparisons

Adjustments for multiplicity will not be made, because no formal statistical testing will be performed in this study.

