3.7. Data Handling Conventions and Transformations

Laboratory data that are continuous in nature but are less than the lower limit of quantitation or above the upper limit of quantitation will be imputed as follows except for urine creatinine:

- A value that is 1 unit less than the limit of quantitation will be used for calculation of descriptive statistics if the datum is reported in the form of “ $< x$ ” (where x is considered the limit of quantitation). For example, if the values are reported as < 50 and < 5.0 , values of 49 and 4.9, respectively, will be used for calculation of summary statistics. An exception to this rule is any value reported as < 1 or < 0.1 , etc. For values reported as < 1 or < 0.1 , a value of 0.9 or 0.09, respectively, will be used for calculation of summary statistics.
- A value that is 1 unit above the limit of quantitation will be used for calculation of descriptive statistics if the datum is reported in the form of “ $> x$ ” (where x is considered the limit of quantitation). Values with decimal points will follow the same logic as above.
- The limit of quantitation will be used for calculation of descriptive statistics if the datum is reported in the form of “ $\leq x$ ” or “ $\geq x$ ” (where x is considered the limit of quantitation).

For urine creatinine, a value of “ < 1 ” is handled as a missing value in its summary and the calculation of related ratios. Urine protein to creatinine ratio (UPCR) is not calculated if the urine protein value (UP) used for the ratio calculation from the same accession number is under the lower limit of quantification (ie, < 4.0 mg/dL).

Logarithm (base 10) transformation will be applied to HIV-1 RNA data for efficacy analysis. HIV-1 RNA results of ‘No HIV-1 RNA detected’ and “ <20 cp/mL HIV-1 RNA Detected” will be imputed as 19 copies/mL for analysis purposes.

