4.1.2. Subject Disposition

The summary of subject disposition will be provided for all screened subjects. This summary will include the number of subjects screened, screen failure subjects who were not enrolled, subjects who met all eligibility criteria but were not enrolled, subjects enrolled, subjects enrolled but not treated, subjects in the Safety Analysis Set, Subjects in the FAS.

In addition, the number and percentage of the subjects from the Safety Analysis Set in the following categories will be summarized:

- Completed study drug
- Prematurely discontinuing study drug (with summary of reasons for discontinuing study treatment)
- Completed study
- Prematurely discontinuing study (with summary of reasons for discontinuing study)

The denominator for the percentages of subjects in each category will be the number of subjects in the Safety Analysis Set.

No inferential statistics will be provided. A data listing of reasons for study drug/study discontinuation will be provided.

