7.2.3. Metabolic Laboratory Evaluations

For metabolic assessments, including fasting glucose and the lipid panel (ie, total cholesterol, triglycerides, LDL, HDL, total cholesterol to HDL ratio), only those measurements under fasting status will be summarized by visit using descriptive statistics. Change from baseline will be tested using the Wilcoxon signed rank test.

In addition, the number and percentage of subjects who took lipid modifying medications at study entry and the number and percentage of subjects who initiated lipid modifying medications during the study will be provided.

A lipid modifying medication is defined as a medication with drug class “LIPID MODIFYING AGENTS” and preferred drug name containing the wording of “STATIN”.

A sensitivity analysis of fasting lipid tests (including total cholesterol, LDL, HDL, triglycerides, and total cholesterol to HDL ratio) will be performed by excluding subjects who took lipid modifying medications at study entry or initiated the medications during the study: baseline, Week 96 and change from baseline at Week 96 will be summarized. Only subjects with both baseline and Week 96 values will be included in the analysis.

Median (Q1, Q3) of change from baseline in fasting metabolic assessments over time will be plotted.

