7.2.5. Renal-Related Laboratory Evaluations

7.2.5.1. Serum Creatinine and eGFR_{CG}

Baseline, postbaseline, and change from baseline in serum creatinine and eGFR_{CG} will be summarized by visit using descriptive statistics.

Median (Q1, Q3) of change from baseline in serum creatinine and eGFR_{CG} over time will be plotted.

7.2.5.2. Urine Creatinine, Urine Retinol Binding Protein to Creatinine Ratio, Beta-2-Microglobulin to Creatinine Ratio, and Urine Protein to Creatinine Ratio

Baseline, postbaseline, and change from baseline in urine creatinine will be summarized by visit using descriptive statistics. Change from baseline will be tested using the Wilcoxon signed rank test.

Baseline, postbaseline, change from baseline, and percentage change from baseline in urine RBP to creatinine ratio and beta-2 microglobulin to creatinine ratio will be summarized by visit using descriptive statistics. Change from baseline and percentage change from baseline will be tested using the Wilcoxon signed rank test.

Subjects will be classified into 4 categories based on their UP and UPCR results: The categories will be (1) UP $< 4.0 \text{ mg/dL}$, (2) UPCR $< 200 \text{ mg/g}$, (3) UPCR $> 200 \text{ mg/g}$, and (4) missing, where UPCR will only be calculated when UP $\geq 4.0 \text{ mg/dL}$. The number and percentage of subjects in each UP and UPCR category will be summarized by baseline category at Weeks 4, 12, 24, 48, 60, 72, 84 and 96.

Median (Q1, Q3) percentage change from baseline in urine RBP to creatinine ratio and beta-2 microglobulin to creatinine ratio over time will be plotted.

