7.3. Body Weight, Height, and Vital Signs

Descriptive statistics will be provided for vital signs and body weight as follows:

- Baseline values
- Values at each postbaseline analysis window
- Change from baseline at each postbaseline analysis window

A baseline value will be defined as the last nonmissing value obtained on or prior to the date of first dose of B/F/TAF. Change from baseline to a postbaseline visit will be defined as the postbaseline value minus the baseline value.

In the case of multiple values in an analysis window, data will be selected for analysis as described in Section 3.8.3. No formal statistical testing is planned.

A by-subject listing of vital signs will be provided by subject ID number and visit in chronological order. In the same listing, a by-subject listing of body weight, height, and BMI will be provided.

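### SAP 3.5 waives multiplicity adjustment because no formal testing is done, yet 7.2.3 and 7.2.5.2 order unlabelled signed rank tests, including one on percentage change that leans toward increases

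*SAP*

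**What the plan says.** SAP 3.5 gives a single reason for not adjusting for multiplicity: "because no formal statistical testing will be performed in this study". It makes no exception for safety data.

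SAP 7.2.3 says that fasting glucose and the lipid panel "will be summarized by visit using descriptive statistics. Change from baseline will be tested using the Wilcoxon signed rank test". SAP 7.2.5.2 orders the same test for urine creatinine. For the retinol binding protein and beta-2 microglobulin to creatinine ratios it says: "Change from baseline and percentage change from baseline will be tested using the Wilcoxon signed rank test".

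Neither section states a significance level or sidedness, or calls the p-values nominal, exploratory or descriptive. Nothing elsewhere in the SAP or protocol does so either. Protocol 8.6.3 plans summaries of laboratory data and names no test.

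Two further statements bear on the count. SAP section 1 says: "The Week 24 analyses and the Week 48 analyses will not be repeated for this final analysis". SAP 7.2.5.2, however, sets out the urine protein categories for the final analysis so that they "will be summarized by baseline category at Weeks 4, 12, 24, 48, 60, 72, 84 and 96".

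**The concern.** The reason given for not adjusting does not match what the SAP orders. A reader of 3.5 would expect no p-values; a programmer following section 7 would produce several dozen. In a single-arm study with no control group, an unlabelled small p-value against baseline can be read as evidence that lipids or tubular markers changed after the switch.

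The second issue holds whatever the word formal means. The signed rank test assumes differences symmetric about zero when nothing has changed. Percentage change cannot fall below -100% and has no upper bound. A halving scores -50% and a doubling +100%, so increases take the larger ranks. The test can therefore signal a rise in a tubular marker when there is none, and it is weak at showing a fall.

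**Working it through.** The plan states no alpha, power or number of tests, so it has no figure to reproduce.

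**Inputs**
- Metabolic measures: 6 (glucose, total cholesterol, triglycerides, LDL, HDL, total cholesterol to HDL ratio; SAP 7.2.3). Post-baseline windows: 3 (Weeks 24, 48, 96; SAP Table 3-2).
- Urine creatinine: 1 measure, 9 windows (SAP Table 3-1, which includes Week 36).
- Urine marker ratios: 2, on 2 scales (SAP 7.2.5.2), 8 windows (SAP Table 3-3).
- n = 86, from the disposition mock-up in SAP Appendix 7. n = 70 is an assumed smaller number with evaluable samples.
- Assumed: two-sided alpha of 0.05, and the SD of log(post/baseline). The documents give neither.

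**Count, tests read as by visit**

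| Reading | Metabolic | Urine creatinine | Ratios | Total |
|---|---|---|---|---|
| All visits | 6 × 3 = 18 | 9 | 2 × 2 × 8 = 32 | 59 |
| Without Weeks 24 and 48 | 6 × 1 = 6 | 7 | 2 × 2 × 6 = 24 | 37 |
| Only visits after Week 48 | 6 × 1 = 6 | 4 | 2 × 2 × 4 = 16 | 26 |

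If urine creatinine follows the eight renal visits, the first two totals are 58 and 36. The urine protein categories list Weeks 4 to 96 for the final analysis, which favours the all-visit reading without settling it.

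**Expected false positives, nothing changing and each test at its level:** k × 0.05
- 59 × 0.05 = 2.95
- 37 × 0.05 = 1.85
- 26 × 0.05 = 1.30

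These expectations do not depend on the correlation between tests.

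**Percentage-change test.** Simulation with 20,000 runs, normal approximation to the signed rank statistic, and a median ratio of 1 (a null of no change on the ratio scale, lognormal data), n = 86:

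| Assumed log-ratio SD | Rejects | False increases | False decreases |
|---|---|---|---|
| 0.1 | about 5% | 4.0% | 1.4% |
| 0.2 | about 7% | 6.3% | 0.9% |
| 0.6 | about 21% | about 21% | about 0.2% |
| 1.0 | about 39% | about 39% | under 0.1% |

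At n = 70 the figures for SD 0.2, 0.6 and 1.0 are about 7%, 18% and 33%. A test on log(post/baseline) stays at about 5% throughout, as it should for lognormal data. With a true 15% fall, SD 0.6 and n = 86, the percentage-change test detects the fall in about 23% of runs and the log-ratio test in about 67%.

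**Absolute-change test.** This holds about 5% if baseline and follow-up values are exchangeable. If the log ratio is instead independent of baseline, it rejects about 6%, 12% to 17% and 22% to 33% at SD 0.2, 0.6 and 1.0 (n = 86, baseline log SD from 1.0 to 0.5).

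**The case against.** The strongest reply is that formal means confirmatory. The study is single-arm, its efficacy results are estimates with confidence intervals, and its sample size rests on feasibility. With no hypothesis or decision rule, there is nothing to adjust. That is a reasonable intention, but the SAP never says it. Section 7.3 uses almost the same phrase, "No formal statistical testing is planned", where no test is ordered, so there it means no testing at all. Even on the sponsor's reading, one clarifying sentence is needed.

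It is tempting to add that several sections without tests say "No inferential statistics will be provided" while 7.2.3 and 7.2.5.2 do not. This shows little: the CD4, liver, serum creatinine, ECG and adherence-scale sections order no test and also lack such a sentence. The contradiction rests on the instruction to test.

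A third objection is that the log ratio performs well because the simulated data are lognormal. That stands. When percentage change is simulated as symmetric about zero (SD 0.2 and 0.4, n = 86), the percentage test holds 4.9% and 5.1%, while the log-ratio test rejects 7.1% and 12.8%. The criticism therefore depends on taking no change to mean a ratio centred on 1. I think that is the natural null for a positive, skewed urine ratio, but it is an assumption.

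**Conclusion.** Section 3.5 is wrong as written and should be brought into line with 7.2.3 and 7.2.5.2. Confidence in the mismatch is high. The number of tests, 59 or 37 and possibly fewer, depends on how the statement about not repeating Weeks 24 and 48 is read.

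Three stronger readings are not supported:
- **A near-certain false positive.** Independence would give 1 - 0.95^59 = 95% and 1 - 0.95^37 = 85%. The tests share baselines, total cholesterol and HDL enter their own ratio, and urine creatinine is the denominator of both marker ratios. The documents give no correlations, and the formula also sets every test at 5%, which the percentage tests may not hold. Only the expected counts, roughly 3 (2), are worth quoting, with the same condition.
- **Percentage-change tests that are always anti-conservative.** Inflation is negligible at a log-ratio SD of 0.1 and large at 0.6 or above; the documents give no variability. The error is also directional: too many increases, too little power for falls.
- **A threat to the trial's conclusions.** No endpoint or decision depends on these tests, and the primary endpoint is reported with a confidence interval. The harm is limited to how metabolic and renal safety statements are read.

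The change is worth making because it is cheap and affects which p-values are reported.

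**What to change.** Make the sections agree, in one of two ways.

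(a) Delete the test sentences in 7.2.3 and 7.2.5.2 and keep the descriptive summaries. Section 3.5 then becomes true.

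(b) Keep the tests, and reword 3.5 to say that the signed rank p-values in 7.2.3 and 7.2.5.2 are nominal, unadjusted and exploratory. For the two urine ratios, drop the percentage-change test or replace it with a signed rank test on log(post/baseline), and show percentage change descriptively. The log ratio should be computable: SAP 3.7 replaces below-limit results by positive values, and a urine creatinine below 1 "is handled as a missing value in its summary and the calculation of related ratios".

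Removing the absolute-change test as well is optional. So are a note in 7.8, a restriction to Week 96, or a Holm adjustment.

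The cost is a few sentences and, if the log ratio is used, one derived variable per ratio. There would be no p-value on the percentage scale. Under (b), dropping the percentage tests leaves 59 - 16 = 43 tests, or 37 - 12 = 25. At 0.05 that is 43 × 0.05 = 2.15, or 25 × 0.05 = 1.25, expected false positives if nothing changes and each test holds its level, so the label is still needed. Replacing them with log-ratio tests leaves the count at 59 or 37.
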